5.3 Control treatment

Patients allocated to the control group receive standard prehospital care, consisting of direct pressure/dressings.

5.4 Other aspects of care

All other aspects of trauma resuscitative care take place according to local protocol, including airway management, provision of supplemental oxygen, intravenous fluid resuscitation, administration of blood products, splinting of extremities, bandaging of wounds and surgical interventions. Upon arrival at the hospital, ED/trauma center personnel perform initial patient assessment according to standard Advanced Trauma Life Support protocols. Patients receive concurrent interventions, including provision of oxygen, insertion of intravenous lines, and infusion of intravenous fluids and blood products.

6. RECRUITMENT

6.1 Setting

The PhoXSTAT trial is conducted in the prehospital setting, by participating Emergency Medicine Service (EMS) providers, and associated level I trauma centers.

6.2 Patients/Study Subjects

The study's entry criteria select patients with life-threatening injuries, as specified under 21 CFR 40.24(a)(1):

6.2.1 Inclusion criteria

- a) Age \geq 15 years or estimated body weight \geq 50 kg.
- b) Penetrating junctional injury (femoral or axillary), with
 - i. visible bleeding
 - ii. too proximal to be controlled with a tourniquet
- c) Class 3 or 4 hemorrhagic shock
- d) Patient will be taken to participating level I trauma center, directly from the scene

6.2.2 Exclusion criteria

- a) Prisoners, children <15 years old, known pregnant patients.
- b) Patients receiving chest compressions (prior to XSTAT[®] use).
- c) Patients with an opt-out bracelet.

Adolescents will be included because children aged 15 and over are typically transported to, and treated, in adult trauma centers. Only children below this age are taken to specialist pediatric trauma centers (when available).

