6.3.2 Trial intervention packs

Each EMS vehicle randomly receives a pre-packaged, sealed, numbered trial intervention pack, consisting of a durable plastic case, which either contains either two XSTAT[®] devices, or is empty. The pack remains on the vehicle until used or expired. When a suitable patient meeting the inclusion criteria for the trial is identified by the EMS providers, the pack is opened. If it contains the device, it is used. Once a pack has been used, it is replaced (when the vehicle returns to its base location).

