6.4.6 Opt-out

The ability and method of "opting out" of the study will be determined by the UAB Institutional Review Board, with updating by the other two sites (USC and VUMC). Because the population eligible for enrollment includes all citizens in the study regions, it will not be possible to target specific individuals, although the UAB IRB may suggest specific age groups and ethnic groups, determined by trauma registry data. Citizens wishing to opt-out of the trial will be provided with an "opt-out" bracelet. EMS personnel will be trained to check for opt-out identifiers prior to enrolling any patient.

6.4.7 "Prospect of direct benefit"

Information from animal and preclinical studies, and early clinical use support the potential for the investigational product to provide a direct benefit to the individual subjects. Participation in this pilot trial holds out the prospect of direct benefit to the subjects because

a) The subjects are in a life-threatening situation that necessitates intervention. Specifically, the condition in question (junctional hemorrhage) is not well-

addressed with currently available treatments, and hemorrhage is frequently not controlled until the patient reaches hospital.

- b) Information from appropriate animal and other preclinical studies support the potential for the intervention to provide a direct benefit to the individual subjects.
- c) The risks associated with the investigation are reasonable in relation to what is known about the medical condition of the potential class of subjects, the risks and benefits of standard therapy, if any, and what is known about the risks and benefits of the proposed intervention or activity.

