10.4 Efficacy

We will compare the intervention (XSTAT[®]) and control groups, with regards to outcomes specified. As this is a pilot/feasibility study, no power or sample size calculation is required.

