Appendix 2: Data Dictionary Codebook

The University of Alabama Ophthalmology Services Foundation

PhoXSTAT

🛄 Codebook 🔻

📖 Data Dictionary Codebook

04/19/2019 1:29pm

r

	 Conapse all instruments 			
	Variable / Field Name	Field Label Field Note	Field Attributes (Field Type, Validation, Choices, Calculations, etc.)	
Instr	strument: Form 5: Randomized to XSTAT (form_5_randomized_to_vstat)			
1	kit_number	Kit label #	text, Identifier	
2	vehicle_id	Vehicle ID #	text	
3	header_f6		descriptive	
4	num_wounds	Section Header: Describe the wounds treated with XSTAT:	radio	
	Show the field ONLY if: [vehicle_id] <> ""	How many wounds were treated with XSTAT?	1 1 2 2	
5	wound_1_loc	Where was the anatomical location of wound #1?	radio	
	Show the field ONLY if: [num_wounds] = '1' or [num_ wounds] = '2'		1 Axilla 2 Groin	
6	wound_1_side	On which side of the body was the wound #1?	radio	
	Show the field ONLY if:		1 Left	
	[num_wounds] = '1' or [num_ wounds] = '2'		2 Right	
7	wound_1_orientation	What was the anatomical orientation of wound #1 (Choose all	checkbox	
	Show the field ONLY if:	that apply)?	1 wound_1_orientation1 Anterior	
	[num_wounds] = '1' or [num_		2 wound_1_orientation2 Posterior	
	wounds] = '2'		3 wound_1_orientation3 Medial	
			4 wound_1_orientation4 Lateral	
8	wound_2_loc	Where was the anatomical location of wound #2?	radio	
	Show the field ONLY if:		1 Axilla	
	[num_wounds] = '2'		2 Groin	
9	wound_2_side	On which side of the body was wound #2?	radio	
	Show the field ONLY if:		1 Left	
	[num_wounds] = '2'		2 Right	
10	wound_2_orientation	What was the anatomical orientation of wound #2 (Choose all	checkbox	
	Show the field ONLY if:	that apply)?	1 wound_2_orientation1 Anterior	
	[num_wounds] = '2'		2 wound_2_orientation2 Posterior	
			3 wound_2_orientation3 Medial	
			4 wound_2_orientation4 Lateral	
11	kit_opened_yn	Section Header: Describe the use of the study protocol:	yesno, Required	
	Show the field ONLY if:	Was kit opened?	1 Yes	
	[num_wounds] = '1' or [num_ wounds] = '2'		0 No	
12	randomized_yn	Was the patient randomized to treatment with XSTAT syringe?	yesno, Required	
	Show the field ONLY if:		1 Yes	
	[kit_opened_yn] = '1'		0 No	

13	xstat_attempted	Was treatment with XSTAT attempted?	yesno, Required		
	Show the field ONLY if: [randomized_yn] = '1'		1 Yes 0 No		
14	violation_reason	Please state reason(s) for protocol violation	notes		
	Show the field ONLY if: [xstat_attempted] = '0' and [r andomized_yn] = '1'				

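### The chest-compression exclusion in 6.2.2(b) is timed to XSTAT use, which only one arm reaches and only after allocation is visible; it should be timed to before the pack is opened

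*Protocol*

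**What the plan says.** Section 6.2.2(b) excludes "Patients receiving chest compressions (prior to XSTAT[®] use"). Section 6.2 introduces the list by saying that the study's "entry criteria select patients with life-threatening injuries".

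On the arms, section 5.3 states: "Patients allocated to the control group receive standard prehospital care, consisting of direct pressure/dressings". Under section 6.3.2 each vehicle carries a sealed pack that holds either two devices or nothing. The order of events is given as "When a suitable patient meeting the inclusion criteria for the trial is identified by the EMS providers, the pack is opened", followed by "If it contains the device, it is used".

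Of the exclusions, only opt-out has an expressly stated moment of checking, in section 6.4.6: "EMS personnel will be trained to check for opt-out identifiers prior to enrolling any patient".

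Section 10.4 plans an arm comparison: "We will compare the intervention (XSTAT[®]) and control groups, with regards to outcomes specified". Objective 2 (section 4.2.1) names admission lactate, admission base deficit and mortality as candidate outcomes for a later trial.

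**The concern.** An eligibility rule should be applied at a moment that every candidate reaches and before anyone knows the allocation. As worded, this one meets neither condition. Device use does not happen in the control arm, and in the XSTAT arm it comes after the crew has seen what the pack contains.

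The condition concerned is also a poor one to leave loose. A need for chest compressions is closely tied to death and to the severity of shock, which lactate and base deficit reflect. If sites settle the question differently in the two arms, patients with the worst prognosis could be counted in one arm and not in the other. With at most 50 patients, each one is visible in the estimates.

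**Working it through.** **Order of events, from sections 5.3, 6.2.2 and 6.3.2**

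| Step | XSTAT arm | Control arm |
|---|---|---|
| Patient judged suitable, pack sealed | reached | reached |
| Pack opened, allocation seen | reached | reached |
| Device used (the moment named in 6.2.2(b)) | reached | never reached |

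The first two steps are common to both arms, and only the first comes before allocation is known. The criterion is attached to the third.

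**Two readings of 6.2.2(b)**

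1. *Baseline check.* The criterion is settled when the patient is judged suitable. This fits the term entry criteria in section 6.2 and the order in 6.3.2. Nothing else then conflicts, but the parenthesis names the wrong moment, and 6.3.2 mentions only the inclusion criteria as the condition for opening.
2. *Literal.* A patient who needs compressions between opening and use is excludable in the XSTAT arm. A control at the same point has no defined status. The XSTAT patient would also be a randomized patient with a protocol-violation reason (Appendix 2, Form 5, fields 12 to 14). The arrest would be a reportable event, because section 14.2 starts reporting at randomization and section 14.3.2 lists cardiac arrest.

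**Size.** The protocol gives no figure for arrests between opening and use, so this is a range under assumptions. Inputs:

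- n = 50/2 = 25 per arm. The maximum of 50 is in section 9; the even split is assumed.
- Mortality m = 7.5% (section 3.1.2, isolated femoral arterial injury, not selected for class 3 or 4 shock), or 30% (assumed).
- f = 1% to 10% of deaths needing compressions in that interval (assumed).

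Expected affected deaths in the XSTAT arm = 25 × m × f. Chance of at least one = 1 − (1 − m × f)^25.

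| m | f | Expected | Chance of at least one |
|---|---|---|---|
| 7.5% | 1% | 0.02 | 1.9% |
| 7.5% | 10% | 0.19 | 17.2% |
| 30% | 1% | 0.08 | 7.2% |
| 30% | 10% | 0.75 | 53.3% |

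In the most extreme row, the chance of two or more is 17.2%.

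Effect of excluding one death from an arm, with exact 95% intervals:

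- 2/25 = 8.0% (1.0 to 26.0) becomes 1/24 = 4.2% (0.1 to 21.1), a shift of 3.8 points.
- 8/25 = 32.0% (14.9 to 53.5) becomes 7/24 = 29.2% (12.6 to 51.1), a shift of 2.8 points.

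Standard error of the arm difference = √(2m(1 − m)/25): 7.4 points at m = 7.5% and 13.0 points at m = 30%. Each shift is well below the corresponding standard error.

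**Form 5 (secondary).** Field 4 asks "How many wounds were treated with XSTAT" and offers only 1 or 2. Field 11 (kit opened) appears only if field 4 is 1 or 2; field 12 (randomized to XSTAT) depends on field 11, field 13 (treatment attempted) on field 12, and field 14 (violation reason) on fields 12 and 13. To record an opened pack without device use, staff must first enter at least one wound as treated with XSTAT. Field 12 allows the answer No, so the same would apply to controls if they are entered on this form.

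**The case against.** The strongest reply is that exclusion criteria are entry conditions by nature. A patient already receiving compressions is not a suitable patient, whichever pack is on board. Form 2 (verification of eligibility) points the same way: all exclusion questions must be answered No, and the items shown carry no condition by arm. The parenthesis may only mean that compressions starting after device use do not exclude retrospectively. Fields 12 to 14 of Form 5 and sections 14.2 and 14.3.2 then look like evidence that randomized patients are kept. This largely stands as an account of intent. It does not repair the wording, which leaves the interval between opening and use undefined for both arms.

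A reader might go further and infer that the protocol contradicts itself, or that it directs the removal of randomized XSTAT patients. The documents do not support that. No section says that a randomized patient is removed because of compressions, and the conflict arises only on the literal reading. Nor can a bias in favour of XSTAT be inferred: the handling of controls is unstated, and one excluded control death shifts the comparison the other way.

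Two further limits are fair. Codebook fields 53 to 83 are not in the available text, so a chest-compression item with its own timing, or another form recording unused packs, may exist there. And detailed analysis populations may be left to a statistical analysis plan. Who counts as enrolled and randomized is different: section 10.1 reports that number as a feasibility result, so its definition belongs in the protocol.

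**Conclusion.** The point holds as a minor wording fault with a real, if narrow, consequence. A shared exclusion is timed to an event that only the XSTAT arm reaches, after allocation is visible, and section 6.3.2 does not close the gap because it names only the inclusion criteria. This conclusion needs no assumptions.

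The size does need them. With an even split of 50 and the assumed compression rates, the likely effect is none or one patient, of unknown direction. The largest figures come from combining the two most extreme assumed values. The trial is a pilot with no primary outcome (section 7), so no confirmatory test is at risk; the effect is confined to the Objective 2 planning estimates and the unpowered comparison in section 10.4.

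The Form 5 display rule is a genuine but secondary fault, subject to what the unseen fields contain.

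**What to change.** - **Section 6.2.2(b):** replace the reference to XSTAT use with one time point common to both arms, before the pack is opened.
- **Section 6.3.2:** state that inclusion and exclusion criteria are both checked before opening, and that every patient whose pack is opened counts as randomized in the allocated arm.
- **Form 5:** let field 11 be answered whatever is entered in field 4, or allow 0 in field 4 and show field 11 for that value too.
- Read sections 14.2 and 14.3.2 and fields 12 to 14 against the new wording so that all describe the same patient in the same way.

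These changes settle only who is counted. Whether the device is used in a patient who arrests after opening is for the investigators to reconcile.

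The cost is one line in 6.2.2, one or two lines in 6.3.2 and one display rule. The downside is that a few patients may be counted in the XSTAT arm without having received the device.

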6.3 Randomization

6.3.1 Randomization by vehicle

Patients are individually randomized, albeit indirectly, by randomizing EMS vehicles. (Given the administrative and logistical difficulties of direct individual randomization in the prehospital setting, this approach is more practical.)

6.3.2 Trial intervention packs

Each EMS vehicle randomly receives a pre-packaged, sealed, numbered trial intervention pack, consisting of a durable plastic case, which either contains either two XSTAT[®] devices, or is empty. The pack remains on the vehicle until used or expired. When a suitable patient meeting the inclusion criteria for the trial is identified by the EMS providers, the pack is opened. If it contains the device, it is used. Once a pack has been used, it is replaced (when the vehicle returns to its base location).

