3.2.3 Operational philosophy

Hemorrhage should be controlled as early as possible, ideally before reaching a trauma center or medical treatment facility. Given its small size, low weight, and ease of application, the XSTAT[®] device is well-suited for prehospital use, in both the civilian and military setting, and this is probably where the device's applicability lies.

There would appear to be less justification for the use of XSTAT[®] in the setting of a trauma center, where patients can be taken directly to an operating room, or have bleeding controlled by other means.

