6.3.3 Tracking labels

The trial intervention packs also contain a tracking label, which must be attached to the patient, to ensure that the trauma center is a) made aware of the patient's enrollment; and b) able to identify which treatment was administered. The tracking label is also used to collect a small amount of prehospital data.

This mechanism avoids having to access a randomization mechanism in real-time and having to carry multiple packs. The disadvantage is that, should a crew encounter more than one suitable patient per shift, some patients may be missed. In addition, in a small study, there is a possibility that, purely by chance, eligible patients may be preferentially encountered by EMS units randomized to either the intervention, or the control treatment. This risk will be reduced with a larger sample size.

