9. RECRUITMENT TARGETS

As PhoXSTAT is a feasibility trial, part of the rationale for which is to ascertain the number of eligible and recruitable subjects, there are no formal recruitment targets. An analysis of registry data from UAB suggests that there are around 10 patients per year who might benefit from XSTAT[®] application. On this basis, we anticipate enrolling a maximum of 50 patients, across the three PhoXSTAT sites, over two years.

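### Control packs are empty cases and section 6.3.2 states no matching to the XSTAT packs, so crews could guess the arm before deciding to enroll

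*Protocol*

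**What the plan says.** Section 6.3.2 describes the allocation mechanism: "Each EMS vehicle randomly receives a pre-packaged, sealed, numbered trial intervention pack, consisting of a durable plastic case". The case holds either two XSTAT "devices, or is empty. The pack remains on the vehicle until used or expired". The trigger for enrollment is the crew's own judgement: "When a suitable patient meeting the inclusion criteria for the trial is identified by the EMS providers, the pack is opened".

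Section 6.3.3 adds one item common to both arms: "The trial intervention packs also contain a tracking label, which must be attached to the patient". A control pack is therefore empty apart from that label and its tie. The same section names two drawbacks of the mechanism. Patients may be missed when a crew meets more than one in a shift, and eligible patients may by chance fall more often to vehicles of one arm, a risk it says shrinks with a larger sample. It does not mention that the arm might be guessed from the unopened pack.

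**The concern.** Concealment requires that the person deciding on enrollment cannot foresee the allocation. Here the crew holds the allocation before it decides. A seal stops anyone looking inside, but it does not equalise weight or movement between a case with two devices and one with only a label.

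Crews have room for discretion. Eligibility is judged at the scene, on visible bleeding, class 3 or 4 shock, and a wound "too proximal to be controlled with a tourniquet". They may also have a reason to use it: under section 5.3 control patients receive standard care, so opening a pack believed to be empty gives the crew no extra treatment to apply.

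If crews guess the arm and act on it, three results are exposed:
- the number entered and randomized (Objective 1, section 7.1);
- the number of forced or non-therapeutic explorations, which section 5.2 treats as a key outcome and which would rise if XSTAT packs were opened for marginal patients;
- the comparison of the arms in section 10.4, together with the baseline outcome estimates under Objective 2.

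Unlike the chance imbalance discussed in section 6.3.3, selection of this kind is systematic, and a larger sample does not remove it.

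**Working it through.** The protocol gives no figure for concealment, so there is nothing to reproduce. The check is a reading of the text, followed by two calculations that rest on stated assumptions.

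**1. What is the same and what differs between sealed packs**
- Same in both arms: a sealed, numbered, durable plastic case and a tracking label (6.3.2, 6.3.3, Appendix 1).
- Different: two devices against none (6.3.2).
- Not stated: case weight, padding, how the devices are held in place, any dummy contents, or whether an empty case carries an expiry date like that of an XSTAT case. Section 11.3 has sites withdraw expired packs, so a difference in expiry dating could be a second cue.

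**2. How long a pack might stay on board**

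Inputs: section 9 says that the lead site's registry "suggests that there are around 10 patients per year who might benefit from XSTAT". It also gives a maximum of 50 patients at three sites over two years, which is 50 / (3 × 2) = 8.3 per site per year. The number of vehicles per site is not stated; 5 to 40 is assumed.

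Mean wait in months = 12 × vehicles per site / eligible patients per site per year, with patients spread evenly over vehicles:

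| Vehicles per site (assumed) | At 10 per year | At 8.3 per year |
|---|---|---|
| 5 | 6.0 | 7.2 |
| 10 | 12.0 | 14.4 |
| 20 | 24.0 | 28.8 |
| 40 | 48.0 | 57.6 |

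Expiry and the two-year enrollment period would cut the longer waits. Across this range a pack is on the vehicle for months before use.

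**3. Hypothetical effect on the split**

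Assume 25 eligible patients per arm, all XSTAT packs opened, and control packs opened at a fraction q of that rate. Control enrolled = 25q, and XSTAT share = 25 / (25 + 25q).

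| q (assumed) | XSTAT | Control | XSTAT share | Total |
|---|---|---|---|---|
| 1.0 | 25 | 25 | 50% | 50 |
| 0.9 | 25 | 22.5 | 53% | 47.5 |
| 0.8 | 25 | 20 | 56% | 45 |
| 0.5 | 25 | 12.5 | 67% | 37.5 |

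No value of q comes from the document.

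**4. Direction of the effect on the count**

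The table covers only under-opening of control packs. Suppose that at q = 0.8 crews also opened XSTAT packs for 5 marginal patients, matching the 25 − 20 = 5 control patients lost. The total would be 30 + 20 = 50, unchanged, while the split would be 60:40. The total could fall, rise or stay the same.

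**5. Whether the trial would notice**

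Section 10.1 reports patients who meet the inclusion criteria as well as those enrolled, but the protocol does not say how eligible patients with unopened packs are found. The label that alerts the trauma center is inside the pack, so an unopened pack leaves none. In the codebook (Appendix 2), the question whether the kit was opened appears only after one or two XSTAT-treated wounds have been entered. The codebook as reproduced is incomplete, so a log may exist elsewhere.

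**The case against.** The strongest reply is that detectability is inferred, not documented. Section 3.2.3 describes the device thus: "Given its small size, low weight, and ease of application". Two light devices, well packed in a rigid case, might not be noticeable. This stands: a reader might infer that crews can tell the arm by weight or rattle, but the text supports only that they could.

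A reader might also infer that one crew handles one case over many shifts. Section 6.3.2 says only that the pack stays on the vehicle. Nothing says that crews stay with a vehicle or handle unopened packs, and the waiting times above depend on an assumed fleet size.

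Pack assembly may be set out in the procedure manual (15.1.2, 16.2.1), which is not shown. So sealing is the only concealment measure that this protocol states, not necessarily the only one used. Still, specifying an empty control case leaves little room for dummy contents.

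The stakes are also lower than in a confirmatory trial. Section 7 names no primary outcome, section 9 sets no formal recruitment target, and section 10.4 makes no power claim. The entry criteria, training on indications (15.1.1) and the eligibility verification form limit opening for marginal patients. These points reduce the weight of the concern. They do not remove it, because the feasibility of prehospital randomization is itself one of the pilot's questions (3.3.2).

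**Conclusion.** The point holds as a weakness in a stated design rule: physically different packs, held by the people who decide on enrollment, with no stated matching. It could select different patients into the arms and affect the enrollment count, the non-therapeutic exploration outcome and the comparison in section 10.4.

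The size cannot be determined from the document. Any split is hypothetical, including the 53% to 67% XSTAT shares above, and the direction of the effect on the total count is unknown. A firm statement that the count is inflated or deflated, or that severity differs by arm, would go beyond the text. The conclusion rests on section 6.3.2 being carried out as written, with no matching specified elsewhere. It is a cheap improvement rather than an error or contradiction in the protocol.

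**What to change.** In section 6.3.2, replace the statement that the control case is empty with: *or contains clearly marked inert filler, so that sealed packs of both arms match in weight, sound, external labelling and expiry date*. Add that pack staff confirm, before release, that sealed packs cannot be told apart by handling.

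The cost is a small amount of filler and a brief check when packs are prepared. The one practical risk is that a crew treating a bleeding patient opens a case with objects in it. The filler must therefore be instantly recognisable as inert, so that it causes no delay; section 13.2 relies on the risk of delay being negligible. Vehicle-based allocation and the care given in either arm stay as they are.
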